## **13.2 PHARMACOKINETICS DATA**

Pharmacokinetic parameter estimates will be calculated by standard noncompartmental methods of analysis.

The following PK parameters will be calculated as appropriate and if possible depending on actual samples collected:  $C_{max}$ ,  $t_{max}$ ,  $C_{min}$  at the end of the dosing interval after each dose in the MAD study, area under the plasma concentration-time curve from 0 to time of last measurable sample (AUC0-last) and area under the plasma concentration-time curve from 0 to infinity (AUC0-∞) in the SAD study, area under the plasma concentration-time curve during the dosing interval (AUC0-Tau) after the first dose and the last dose in the MAD study, CL, CLR, Vz, t1/2, and accumulation ratio for Cmax (RCmax) and AUC(0-∞) [RAUC(0-∞]].

Renal clearance will be calculated as the ratio of amount excreted/AUC. This will be compared to the unbound glomerular filtration rate, which is estimated using creatinine clearance.

Dose proportionality will be evaluated using a regression analysis model to assess the linear relationship between the exposure parameters ( $C_{max}$  and  $AUC_{0-\infty}$  or  $AUC_{0-last}$  from the SAD study;  $C_{max}$  and  $AUC_{0-Tau}$  from the MAD study) and dose as a covariate after

log-transformation (Ln) of the data, according to the equation Ln (exposure parameter) =  $\beta 0 + \beta 1 \times \text{Ln}$  (dose); dose proportionality will be established if the estimated values of the slope ( $\beta 1$ ) are close to 1 and the 95% confidence intervals for the dose-dependent parameters include the value of 1 (12).

An assessment of steady state will be performed using trough concentrations ( $C_{min}$ ) from days 4, 7, 10, and 12 in the MAD study. The ratio of geometric mean of  $C_{min}$  on each corresponding day, divided by the geometric mean of the pooled  $C_{min}$  from the following days will be calculated according to established methods (13, 14). The first assessment timepoint with a calculated  $C_{min}$  ratio that does not statistically differ from a value of 1 will be defined as the timepoint at which steady state is achieved (13, 14).

An interim PK analysis is planned after cohorts 1 and 2 of the SAD study to assess drug exposures. Additional interim PK analyses may be performed based on the results of the interim analyses performed following cohorts 1 and 2. Details of the interim PK analysis will be described in the PK Analysis Plan.

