### **Duration of patient participation in study:**

Participants in the SAD study: each Subject will participate in one treatment period. A treatment period consists of residential stay on days -1 to 2 inclusive with 1 follow up visit (Day 3) and phone call (Day 5-8).

Participants in the MAD study: each Subject will participate in one treatment period. A treatment period consists of residential stay on days -1 to 5, with discharge the morning of day 5 and re-admission on day 712 inclusive with 1 follow up phone call (Day 15) and phone call (Day 17-19).

Participants in the CSF capture study: each Subject will participate in one treatment period. A treatment period consists of residential stay on days -1 to 2 inclusive with 1 follow up visit (Day 3) and phone call (Day 5-8).

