#### Table 1: SAD schedule of assessments and procedures

An early termination visit will be scheduled on an ad hoc basis for any subject who withdraws from the study. \* Physical examinations can be conducted at any additional time at the judgement of the Principal Investigator (eg, to evaluate an adverse event)

^FSH for postmenopausal women at screening visit

\*\* Day 1 Timepoints: 1-hr preinfusion, and 1, 2, 4, 8, and 12 hr after the start of the infusion.

\*\*\* Ocular examinations include visual acuity and color vision tests.

\*\*\*\* On Day 1, MOAA/S is performed preinfusion, during the infusion at approximately 20 min after start of infusion, 40 min after start of infusion, and approximately 1 hr after the start of the infusion.

\*\*\*\*\* On Day 1, CADSS is performed preinfusion and approximately 40 min and 80 min after the start of the infusion.

Procedure	Screening					Confin	ement					Follo	ow-Up
	(Day -28 to Day -2)	Day -1	Day 1	Day 2	Day 4	Day 5	Day 7	Day 8	Day 9	Day 11	Day 12	Day 15	Day 17-19
Informed Consent	X												
Eligibility Criteria	X	X											
Demographics	X												
Height	X												
Weight, BMI	X	X									Х		
Medical history	X	X									Χ	X	X
Physical Examination*	X	X					Χ				Χ		
Vital Signs**	X	X	Х		X	X	X	X	X	X	X		
ECG**	X	X	Х		X	X	X	X	X	X	X		
Urine Drug Test	X	X					X						
Alcohol Breath Test	X	X					X						
Pregnancy Test	X	X					X						
(Females)^													
Serology (Hepatitis C,	X												
Hepatitis B, HIV)													
Clinical Lab. Tests	Х		Х	Х				Х	Х	Х	Х		
(Hema., Chem.,													
Urinalysis)													
Prior and Concom. Meds.	X	X	X			X	X				X	X	X
Ocular Examinations***		X		X						X	X		
Modified Observer's			Х		Х			Х		Х			
Assess. of Alert./Sed.													
(MOAA/S)****													
Suicide Screening (C- SSRS)	X	X	X	X	X	X	X	X	X	X	X	X	X
Mood and Cognitive		X	X	X	X	X	X	X	X	X	X	X	X
Assessment (POMS)													
Clin. Admin. Diss. States			X		X			X		X			
Scale (CADSS)*****													
IV Drug Administration			X		X			X		X			
Blood Sample Coll. (PK)			X	X	X			X		X	X		
Check-in & Confinement		X	X	X	X		X	X	X	X			
Check-out*****						X					X		
Adverse Events			X	X	X	X		X	X	X	X	X	X
Outpatient Visit													
Phone Call												X	Х

Table 2: MAD schedule of assessments and procedures

An early termination visit will be scheduled on an ad hoc basis for any subject who withdraws from the study.

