#### Table 4: SAD planned dosing levels

### 6.0 STUDY DESIGN (MAD)

The multiple ascending dose (MAD) portion of the study is a 2-cohort single site, double-blind, placebo-controlled design assessing (2R,6R)-Hydroxynorketamine in healthy adult male and female volunteers. All Subjects in the MAD study will undergo a screening period of up to 28 days to ensure that all eligibility requirements are met. Key baseline safety metrics will be taken during screening and on the first Day of confinement. Selected safety metrics will be collected during the on-drug portion of the study. A final safety assessment will be conducted via an outpatient visit and follow-up phone call.

All cohorts will include 6 Subjects receiving drug and 2 Subjects receiving placebo. Each Subject will receive a total of 4 doses (drug or placebo) administered on days 1, 4, 8, and 11. Each Subject will only participate in a single dose level. Table 5 outlines the planned dosing levels and number of Subjects in each cohort.

Each dose will be administered after Subjects have fasted overnight for at least 8 hours.

Safety monitoring and assessments will be performed as described in sections 8.7 and 12.8. AE monitoring and reporting will be performed as described in sections 8.7 and 12.8. Dosing may be stopped if any of the stopping criteria are met as described in section 10.3. Determination of whether to escalate to the next dose level if stopping criteria are met will be made by the PI in consultation with the Medical Monitor and the Study Sponsor.

Pharmacokinetic blood samples will be collected as described in section 8.6.

Cohort	Dose (mg/kg)	Subjects on Active Drug (n)	Subjects on Placebo (n)
1	1.0	6	2
2	2.0	6	2

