# **8.6 PHARMACOKINETIC EVALUATION**

Blood samples will be obtained during the study for measurement of (2R,6R)-Hydroxynorketamine plasma concentrations to provide an unambiguous association between drug dose and systemic drug exposure. Serial PK blood samples will be collected during the SAD and MAD studies for each Subject receiving drug and placebo at 9 timepoints and 20 timepoints, respectively. For PK assessments, there will be an acceptable blood collection window of  $\pm$  5 minutes in the first 8 hours after a dose and  $\pm$  30 minutes thereafter.

Serial PK blood samples will be collected during the SAD portion for each Subject receiving drug and placebo at 9 timepoints (preinfusion, end-of-infusion [approximately 40 minutes], 1, 2, 4, 8, 12, 24, and approximately 48 hr after the start of the infusion). Pharmacokinetic urine samples (up to 3 per Subject) will be collected during the SAD study for each Subject receiving drug and placebo at set intervals following the initiation-of-infusion (0-4, >4-8, >8-12, >12-24 hr).

Serial PK blood samples will be collected for the first and fourth (last) dosing in the MAD study for each Subject receiving drug and placebo. Blood PK samples will be obtained at 8 timepoints (preinfusion, end-of-infusion [approximately 40 minutes], 1, 2, 4, 8, 12, and approximately 24 hr after the start of the infusion). Two PK blood samples will be collected for the second and third dosing in the MAD study for each Subject receiving drug and placebo at preinfusion and end-of-infusion [approximately 40 minutes] timepoints.

Serial PK blood samples will be collected during the CSF Capture portion for each Subject receiving drug and placebo at 8 timepoints (preinfusion, end-of-infusion [approximately 40 minutes], 1, 2, 4, 8, 12, and approximately 24 hr after the start of the infusion). CSF samples will be collected during the CSF Capture portion for each Subject receiving drug and placebo at 3 timepoints (preinfusion, 1, and approximately 8 hr after the start of the infusion).

Blood and CSF samples will be stored and shipped to LabCorp (Covance) central laboratories who will perform PK analysis of (2R,6R)-Hydroxynorketamine using a LC/MS/MS method to determine plasma concentration levels in order to calculate the following PK parameters: Cmax, tmax, Cmin, AUC0-∞, AUC0-Tau, CL, Vz, CLR, t1/2.

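### The MAD steady-state rule in protocol section 13.2 uses trough days on which no sample is drawn, and on the real samples it compares different times after a dose

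*Protocol*

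**What the plan says.** Section 13.2 of the protocol takes Cmin "from days 4, 7, 10, and 12 in the MAD study". For each of those days it divides the geometric mean Cmin by the geometric mean of the pooled Cmin from the days that follow. The first ratio "that does not statistically differ from a value of 1 will be defined as the timepoint at which steady state is achieved". The same section says that Cmin is obtained "at the end of the dosing interval after each dose in the MAD study".

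The sampling is set out elsewhere:

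- **Doses** (section 6.0): "Each Subject will receive a total of 4 doses (drug or placebo) administered on days 1, 4, 8, and 11".
- **Number of draws** (section 8.6): SAD and MAD blood is taken "at 9 timepoints and 20 timepoints, respectively". Doses 1 and 4 have eight draws each, the last at about 24 hours. For the middle doses, "Two PK blood samples will be collected for the second and third dosing in the MAD study", before and at the end of the infusion.
- **Days** (protocol Table 2 and its copy in SAP section 3.2): PK blood is marked on Days 1, 2, 4, 8, 11 and 12. Day 7 is blank for PK, and there is no Day 10 column.
- **Volumes** (Table 10): the second 24-hour draw is labelled Day 11, where Table 2 has Day 12.
- **Follow-up** (synopsis and Table 2): after Day 12 the only contacts are phone calls, on Day 15 and Days 17-19.

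The SAP sends PK analysis to a separate PK Analysis Plan (SAP sections 6.3, 8.2.1 and 9.2).

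**The concern.** The four days in the rule do not match the dosing and sampling days. If two of the named troughs do not exist and a third is not a trough, the analyst has to improvise, and the obvious substitutes lie at different times after a dose. A ratio of such samples reflects how far the concentration has fallen since the dose as well as any accumulation.

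The rule also accepts steady state when a test fails to reject, so small numbers and noisy data favour a positive finding.

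MAD pharmacokinetics is a primary objective, and this is the only rule section 13.2 gives for judging steady state.

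**Working it through.** **1. Reproduce the stated 20 draws**

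| Dose | Draws | Study days on which they fall |
|---|---|---|
| 1 (Day 1) | 8 | seven on Day 1, one on Day 2 |
| 2 (Day 4) | 2 | Day 4 |
| 3 (Day 8) | 2 | Day 8 |
| 4 (Day 11) | 8 | seven on Day 11, one on Day 12 |

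8 + 2 + 2 + 8 = 20, as section 8.6 states. The PK column of Table 10 agrees: 20 + 20 + (5 × 10) + 10 = 100 mL, and 100 / 5 = 20 draws. None is left over for Day 7 or Day 10.

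**2. Try to rescue the day list by relabelling**

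The three later pre-dose draws and the final 24-hour draw are on study days 4, 8, 11 and 12. Counted as days elapsed since dose 1, they are 3, 7, 10 and 11. Neither count gives 4, 7, 10, 12.

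**3. Time after the last dose**

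Doses are at 0, 72, 168 and 240 h.

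- Day 4 pre-dose: 72 − 0 = 72 h
- Day 8 pre-dose: 168 − 72 = 96 h
- Day 11 pre-dose: 240 − 168 = 72 h
- Day 12: 264 − 240 = 24 h

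A further end-of-interval sample, 72 or 96 h after dose 4, would fall on Day 14 or 15. No visit exists then.

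Steps 1 to 3 use the documents only. Steps 4 to 6 are illustrations. The half-life, CV and form of test are assumptions, because the documents give none of them.

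**4. Expected ratios on the real draws**

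Assume one-compartment linear PK with half-life h: C(t) = Σ 2^(−(t − tᵢ)/h) over earlier doses. The infusion multiplies every term by the same constant, so it cancels in ratios.

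For h = 12 h:

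- C4 = 2^−6 = 0.01563
- C8 = 2^−8 + 2^−14 = 0.00397
- C11 = 2^−6 + 2^−14 + 2^−20 = 0.01569
- C12 = 2^−2 + 2^−8 + 2^−16 + 2^−22 = 0.2539

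The three ratios are:

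- Day 4: C4 / (C8·C11·C12)^(1/3) = 0.62
- Day 8: C8 / (C11·C12)^(1/2) = 0.063
- Day 11: C11 / C12 = 0.062

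| Half-life | Day 4 | Day 8 | Day 11 | True 72-h accumulation (Day 11 / Day 4) |
|---|---|---|---|---|
| 6 h | 0.40 | 0.004 | 0.004 | 1.00 |
| 12 h | 0.62 | 0.063 | 0.062 | 1.00 |
| 24 h | 0.72 | 0.26 | 0.24 | 1.07 |

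With dosing continued to exact periodic steady state and h = 12 h, the ratios are still 0.63, 0.063 and 0.062. Dropping Day 12 does not help: at 12 h, Day 8 / Day 11 = 0.25, and Day 4 over pooled Days 8 and 11 = 1.98.

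**5. What the rule would conclude**

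This uses simulated cohorts, paired log-scale t-tests at two-sided 0.05, all samples quantifiable, n = 6 and CV 20-50%. Steady state is never declared in 91-100% of trials (6 h), 41-98% (12 h) and 23-81% (24 h). Nearly all the rest declare it at Day 4. At 24 h, where the Day 4 ratio is truly 0.72, it passes in about 50% of trials at CV 30% and 76% at CV 50%. At h = 12 h and CV 30%, moving from n = 6 to n = 12 raises the never-declared share from 77% to 99%, while the matched Day 4 against Day 11 comparison is non-significant in about 95% at either size.

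**6. Precision of a matched ratio**

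Factor = exp(t × √2 × s / √n), with s = √ln(1 + CV²). For n = 6 and a 90% interval, t = 2.015. CV 20% gives s = 0.198 and a factor of exp(0.230) = 1.26. CV 50% gives s = 0.472 and exp(0.550) = 1.73. For n = 12 the factors are 1.16 and 1.41.

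**The case against.** - **It may be mostly a labelling slip.** The 7 and 10 do match the Day 8 and Day 11 pre-dose draws if days are counted from dose 1. That is fair, but the 4 and 12 then fail, and correct labels still leave 72, 96, 72 and 24 h.
- **The PK Analysis Plan may correct it.** It may, and it was not available. The defect is therefore established for the protocol text. What the final analysis will do remains unknown. Section 13.2 does limit its PK parameters, including Cmin, to what the collected samples allow, but that does not equalise times after dose.
- **The simulation tests a reconstructed rule.** Section 13.2 names no test and cites published methods. The results hold only for half-lives of 6-24 h. At 48-72 h real accumulation is 1.34-1.60. At 72 h with n = 6 and CV 50%, about 47% of trials declare at Day 4 and 42% later, so the outcome is then not driven by sampling time alone. At 6 h the 96-h trough is about 0.002% of the end-of-infusion level and probably not measurable, so the likelier outcome is no result.
- **Little depends on it.** Steady state is not a listed endpoint or an escalation criterion, and accumulation ratios are planned separately. This stands, and it limits the severity.

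**Conclusion.** The point holds as a correction that should be made. From the documents alone, two of the four named days have no sample, a third is a 24-hour post-dose level, and only Day 4 is both named and a real pre-dose trough. Relabelling does not repair the rule, because every ratio then mixes times after dose. For a drug that barely accumulates (half-life 6-24 h, assumed), the relabelled rule could report that steady state was not reached, pass at Day 4 through low power, or give no result if late troughs fall below quantification. Confidence is high on the mismatch. The simulated percentages are illustrative. The consequence is confined to one descriptive PK conclusion.

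**What to change.** 1. Reconcile the days in section 13.2 with Tables 2 and 10, including Table 10's Day 11 label for the last 24-hour draw.
2. Replace the rule with within-subject geometric mean ratios at matched times: Day 12 over Day 2 (both 24 h) as the main comparison, since these samples are the most likely to be measurable, and pre-dose Day 11 over pre-dose Day 4 (both 72 h) where quantifiable. SAD concentration data can confirm that order. Do not pool the 96-h Day 8 trough or the Day 12 sample with the 72-h troughs.
3. Report the ratios with 90% intervals as descriptive estimates, with no pass/fail and no named day of steady state. If 95% is preferred, to match the alpha of 0.05 in SAP section 7, the n = 6 factors become 1.34-2.02.
4. State how values below quantification are handled, for example by using only subjects with both samples quantifiable and reporting how many are not.
5. As a separate point, sampling after dose 4 stops at 24 h, so base the AUC accumulation ratio on AUC0-24 for Day 11 over Day 1, where sampling is identical.

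**Cost:** wording in section 13.2, Table 10 and the PK Analysis Plan, made through a formal amendment with at least IRB notification (section 14.4). No new samples, visits or subjects are needed. The plan gives up naming a day of steady state, and precision is modest.

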# 13.3 qEEG DATA

Quantitative EEG (qEEG) data will be obtained for all study subjects in the SAD cohorts. This data will be collected over approximately 3 hours with predefined resting-state and visual evoked potential intervals. Analysis of the EEG data will include preliminary artifact correction using PCA-based techniques to identify biological artifacts that are not attributed to cortical activity. This will include scrutiny of the component spectral and spatial profiles, ultimately eliminating components that present with nontypical cortical activity. The qEEG parameters that will be studied include the ones discussed below. Other qEEG parameters may be evaluated postacquisition and will be described in the Statistical Analysis Plan.

## Relative spectral power

An FFT analysis will be performed on the raw EEG. From this FFT analysis, the absolute and relative power spectrum will be determined across all frequency bands (delta, theta, alpha, beta and gamma).

## Visual evoked time-locked data

Analysis of sensory processing will be conducted through consideration of the visual evoked potential to a contrast reversing checkerboard. Time-locked, event-related potential will be calculated on the continuous EEG collected during the visual stimulation allowing for high temporal resolution of signals from the primary and secondary visual cortices. Past research has linked these potential to gain control mechanisms in the brain, and analysis of the amplitude and latency effects of infusion will be considered in this context.

# Source localization

Frequency-specific and time-locked source localization will be performed using sLORETA within regions-of-interest specifying Default Mode, Central Executive, and Somatosensory networks.

## 14.0 ADMINISTRATIVE CONSIDERATIONS AND REQUIREMENTS

## **14.1 BASIC PRINCIPLES**

This research will be carried out in accordance with the protocol, the ICH Guideline for Good Clinical Practice: Consolidated Guidance (E6), and applicable regulatory requirement(s) including clinical research guidelines established by the Basic Principles defined in the U.S. 21 CFR Parts 50, 56, and 312, and the Principles enunciated in the Declaration of Helsinki (revised version Fortaleza 2013).

#### 14.2 INSTITUTIONAL REVIEW BOARD, ETHICAL COMPLIANCE, INVESTIGATOR RESPONSIBILTIES, AND SPONSOR RESPONSIBILITIES

This study is being conducted to evaluate the safe-dose ranges and PK of (2R,6R)-Hydroxynorketamine after slow-IV administration to healthy Subjects. The results of this study will provide useful information on dose and exposure of (2R,6R)-Hydroxynorketamine by this mode of administration.

The primary ethical concerns of this study are that this study will be performed in healthy Subjects who will receive no benefit from participation in the study, except for financial compensation for the time and inconveniences that may arise from participation in the study.

As with all clinical studies, there are risks associated with the clinical procedures. To avoid unnecessary risks, methods including the dosing strategy and blood sample collection scheme were designed to minimize the number of venipunctures required to complete the study. Further, the total volume of blood draws in support of clinical laboratory testing and PK evaluations collected from each Subject during the study does not exceed acceptable amount of blood to be collected over the defined time periods as recommended by standards set by the American Red Cross.

Potential Subjects will be fully informed of the risks and requirements of the study and, during the study, Subjects will be given any new information that may affect their decision to continue participation. They will be told that their consent to participate in the study is voluntary and may be withdrawn at any time with no reason given and without penalty or loss of benefits to which they would otherwise be entitled. Only Subjects who are fully able to understand the risks, benefits, and potential AEs of the study, and provide their consent voluntarily will be enrolled.

Any woman who is pregnant, breast feeding, or planning to become pregnant during the study will be excluded from participating in the study. Potential female Subjects must be postmenopausal, sterile, abstinent, or, if heterosexually active, be practicing a highly effective method of birth control before entry and throughout the study. Women, who are not heterosexually active at Screening, must agree to utilize a highly effective method of birth control if they become heterosexually active during their participation in the study.

The PI is responsible for ensuring that the clinical study is performed in accordance with the protocol, current ICH guidelines on Good Clinical Practice (GCP), and applicable regulatory and country-specific requirements.

The GCP is an international ethical and scientific quality standard for designing, conducting, recording, and reporting studies that involve the participation of human Subjects. Compliance with this standard provides public assurance that the rights, safety, and well-being of study Subjects are protected, consistent with the Principals that originated in the Declaration of Helsinki and that the clinical study data are credible.

Before the start of the study, the PI (or sponsor where required) will provide the IEC/IRB with current and complete copies of the following documents:

- Final protocol and, if applicable, amendments.
- Sponsor-approved informed consent form (and any other written materials to be provided to the Subjects).
- Investigator's Brochure (or equivalent information) and amendments/addenda
- Sponsor-approved Subject recruiting materials.
- Information on compensation for study-related injuries or payment to Subjects for participation in the study, if applicable.
- Investigator's curriculum vitae or equivalent information (unless not required, as documented by the IEC/IRB).
- Information regarding funding, name of the sponsor, institutional affiliations, other potential conflicts of interest, and incentives for Subjects.
- Any other documents that the IEC/IRB requests to fulfill its obligation.

This study will be undertaken only after the IEC/IRB has given full approval of the final protocol, amendments (if any), the informed consent form, applicable recruiting materials, and Subject compensation programs, and the sponsor has received a copy of this approval. This approval letter must be dated and must clearly identify the IEC/IRB and the documents being approved.

During the study, the PI (or sponsor where required) will send the following documents and updates to the IEC/IRB for their review and approval, where appropriate:

- Protocol amendments.
- Revision(s) to informed consent form and any other written materials to be provided to Subjects.
- If applicable, new or revised Subject recruiting materials approved by the sponsor.
- Revisions to compensation for study-related injuries or payment to Subjects for participation in the study, if applicable.
- New edition(s) of the Investigator's Brochure and amendments/addenda.
- Summaries of the status of the study at intervals stipulated in guidelines of the IEC/IRB (at least annually).

- Reports of AEs that are serious, unlisted/unexpected, and associated with the investigational drug.
- New information that may adversely affect the safety of the Subjects or the conduct of the study.
- Deviations from or changes to the protocol to eliminate immediate hazards to the Subjects.
- Report of deaths of Subjects under the Investigator's care.
- Notification if a new Investigator is responsible for the study at the site.
- Annual Safety Report and Line Listings, where applicable.
- Any other requirements of the IEC/IRB.

For all protocol amendments (excluding the ones that are purely administrative, with no consequences for Subjects, data, or study conduct), the amendment and applicable informed consent form revisions must be submitted promptly to the IEC/IRB for review and approval before implementation of the change(s).

At least once a year, the IEC/IRB will be asked to review and reapprove this clinical study. The reapproval should be documented in writing (excluding the ones that are purely administrative, with no consequences for Subjects, data, or study conduct).

At the end of the study, the Investigator (or sponsor where required) will notify the IEC/IRB about the study completion.

